4.2.2 Evening before the sleep study

Upon arrival at the clinic, the participant will be asked to sign an informed consent.

The following activities will also occur:

- Document demographics and medical history, including medications.
- Review previous two-month sleep data from the participant's CPAP.
- Height, weight, vital signs will be measured once.
- Pre-sleep questionnaire (which includes recent sleep history for the last 2-3 nights, medications, caffeinated beverages, and alcohol consumption)
- Randomization

4.2.3 In-laboratory overnight PSG

The PSG will be conducted with a split-night design, i.e., approximately 3.5 hours on CPAP and 3.5 hours on TPAP, in random order. The switch between CPAP and TPAP will be operated through the interface screen on the TPAP device. During testing, no expiratory pressure relief will be used during CPAP regardless of such use during normal therapy at home. All patients will be asked to bring in the mask they normally use at night so that it can be used in the study, and the patients will be tested using two 1.8 m lengths of 22 mm tubing to prevent cross contamination. A commercial humidifier will be used to provide humidification since humidification is not supplied with the TheraPAP prototype.

4.2.3.1 Risk-benefit analysis

The procedures involved in the overnight study are similar to clinical routinary activities performed in the laboratory weekly, and therefore the study risk is minimal, with the only risks being related to the following:

- Due to the monitoring equipment used in the lab and the different pressure delivery with TPAP, the participant may sleep poorly and be fatigued the following day.
- If TPAP does not optimally treat the sleep apnea, the patient may have more apneas/hypopneas during the study than occur on CPAP at home. However, a single night of sub-optimally treated sleep apnea poses no real medical risk.

Regarding benefits to the participants:

- During the CPAP portion of the study, the lab personnel will be able to evaluate whether the participant's current treatment at home is adequate. If increased respiratory events during the CPAP portion of the study are found, the settings on the participant's CPAP can be adjusted at home or other corrections could be recommended. Also, since the participants will be monitored as during a normal sleep study, evidence of other sleep disorders or heart disease could be identified and then addressed.
- The results of the study could yield future benefit to the participants in terms of wider treatment alternatives for their OSA.

4.2.4 Morning after the sleep study

The following activities will occur:

- Vital signs will be measured once.
- Post-sleep questionnaire.
- Overall quantification and recording of any adverse event or serious adverse events related to the overnight procedures.

4.3 End of Study Definition

A participant is considered to have completed the study if they have completed all evening, overnight and morning procedures.

5 Study Population

Eligible participants will be recruited from the existing clinic population at the study site. Participants must be able to provide written consent and meet all the inclusion criteria and none of the exclusion criteria.

5.1 Inclusion Criteria

5.1.1 Age and Sex

1. Between 18 to 70 years of age, inclusive.

5.1.2 OSA Measures

2. AHI > 10 on a previous PSG or HST.
3. CPAP adherence for an average of 5 hours/night in the two months before the study

5.1.3 Weight

4. BMI above 18 kg/m², inclusive.

5.1.4 Informed Consent

5. Participant voluntarily agrees to participate in this study and signs an Institutional Review Board (IRB)-approved informed consent prior to performing any of the study-related procedures.
6. Participant must be able to understand the nature of the study and must have the opportunity to have any questions answered.

5.2 Exclusion Criteria

Participants are excluded from the study if any of the following criteria apply:

5.2.1 Medical Conditions

1. Current clinically significant sleep disorder other than OSA of a severity that would interfere with study participation or interpretability of data (including central sleep apnea, per central AHI > 5 events/hour).
2. Current clinically unstable cardiac disease (e.g., rhythm disturbances, coronary artery disease or cardiac failure) or poorly controlled hypertension (>140/90mmHg).
3. Current clinically significant neurological disorder, including epilepsy/convulsions.

4. Other serious major organ system diseases include renal failure, lung disease, neuromuscular disease, or liver disease.
5. Schizophrenia, schizoaffective disorder, or bipolar disorder according to Diagnostic and Statistical Manual of Mental Disorders-5 (DSM-5) or International Classification of Disease tenth edition criteria.
6. Attempted suicide within 1 year prior to screening, or current suicidal ideation.
7. History of substance use disorder as defined in DSM-V within 24 months prior to Screening Visit.
8. A serious illness or infection in the past 30 days.
9. Clinically significant cognitive dysfunction as determined by investigator.

5.2.2 Prior/Concomitant Therapy

10. Chronic oxygen therapy.
11. Patients with hypoglossal nerve stimulation implant.

5.2.3 Other Exclusions

12. Any condition that in the investigator's opinion would present an unreasonable risk to the participant, or which would interfere with their participation in the study or confound study interpretation.

5.3 Screen Failures

Patients that do not meet the inclusion/exclusion criteria at the outpatient screening visit will not be invited to or further contacted to participate in the study.

5.4 Preparation/Handling/Storage/Accountability

Devices will be provided by the sponsor and will be kept in locked designated sleep rooms in each laboratory facility along with the other sleep lab equipment in each room, accessible only from the laboratory personnel. They will be used only for approved study purposes as designated by the sleep lab coordinator who will oversee their use in the sleep lab.

5.5 Measures to Minimize Bias

Each participant will begin the study in one of the treatment arms, (either CPAP or TPAP). The starting treatment arm is determined by a random number generator, as described in Section 7.2. All participants will start on CPAP until they fall asleep, then they will be switched to their designated therapy arm.

5.6 Concomitant Therapy

Usual therapy is allowed as indicated by the patient's general practitioner, except for oxygen therapy, which is an exclusion criterion.

5.7 Discontinuation of Study Treatment

If a clinically significant finding is identified, the Investigator or qualified designee will determine if the participant can continue in the study and if any change in participant management is needed. Any new clinically relevant finding should be reported as an adverse event (AE).

5.8 Stopping Criteria

5.8.1 Individual Participant Stopping Criteria

Participants reporting any SAE considered possibly related or related to study device will be withdrawn from the study.

Any other AE that in the judgment of the Investigator necessitates the participant stopping to protect participant safety, will result in early withdrawal from the study.

5.9 Participant Discontinuation/Withdrawal from the Study

A participant may withdraw from the study at any time at his/her own request or may be withdrawn at any time at the discretion of the Investigator for safety, behavioral, or administrative reasons.

If the participant withdraws consent, the Sponsor may retain and continue to use any data collected before such a withdrawal of consent.

All participants who withdraw from the study with an ongoing AE must be followed until the event is resolved or deemed stable.

Participation may be terminated before completing the study and the reason recorded as follows:

- Withdrawal due to AE
- Participant withdrew consent at their own request, (e.g., intolerance to study procedures)
- At the discretion of the Investigator for safety, behavioral, or administrative reasons
- Other reasons, as they occur

5.10 Participant compensation

Participants will be compensated for their time and participation with a free mask (approximately \$100 value).

6 Study Assessments and Procedures

Study procedures and their timing are summarized in the SoA.

Adherence to the study design requirements, including those specified in the SoA, is essential and required for study conduct.

All screening evaluations must be completed and reviewed to confirm that potential participants meet all eligibility criteria. The Investigator will maintain a screening log to record details of all participants screened and to confirm eligibility or record reasons for screening failure, as applicable.

6.1 Overnight study

- **Methods:** Standard overnight PSG recording, and data interpretation will be performed in accordance with the American Academy of Sleep Medicine (AASM) scoring manual. Participants will be instrumented with standard PSG electrodes and their usual at-home CPAP mask. This setup includes a finger pulse oximeter, chest and abdominal bands, EKG electrodes, a snore sensor on the neck, and anterior tibialis EMG electrodes. A manometer will be added between the end of the tube and the mask connecting tube to measure the participant's pressure directly, and its analog output will feed into the PSG device. The patient flow signal will be extracted from the flowmeter embedded in TheraPAP device filtering off the leak flow from total flow (output). This TheraPAP flowmeter data will be directed to the DC input on the polysomnogram, generating a real-time signal. This signal can be viewed in the control room. A panoramic of the setup in the patient room is shown in figure 2.

[figure not shown]

Figure 1. Continuous positive airway pressure (PAP)/TheraPAP circuit. TPAP, TheraPAP device. PSG, polysomnography.

Patients will report to the laboratory approximately two hours prior to their usual bedtime. Patients will be instructed not to drink alcohol or caffeinated beverages on the night of the

study. Time of lights out will be established according to the participant's approximate habitual bedtime. The participants will be given at least seven hours of time in bed (undergoing either CPAP or TPAP).

- Participants should be actively encouraged to spend at least 1/3 of the night in the supine position and at least 1/3 of the night in the lateral position on each night of study.
- Scoring: PSG studies will be scored for purposes of study endpoints by a registered PSG technician, blinded to treatment assignment.

6.2 Safety Assessments

Planned time points for all safety assessments are provided in the SoA.

Safety assessments will include measurement of vital signs, monitoring and recording of AEs, SAEs, and recording of study or treatment discontinuations. Effects on OSA and sleep parameters (e.g., sleep time and sleep stages) will also be monitored by PSG.

6.2.1 Vital Signs

Assessment of vital signs (seated blood pressure, pulse rate, body temperature, respiratory rate) will be performed at the time points indicated in the SoA.

Vital signs will be measured in a seated position after 5 minutes rest and will include temperature, respiratory rate, systolic and diastolic blood pressure, and pulse. Measurements will be made only once.

6.3 Adverse Events and Serious Adverse Events

The definitions of AEs and SAEs can be found in

Appendix .

Adverse events will be reported by the participant.

The Investigator and any qualified designees are responsible for detecting, documenting, and reporting events that meet the definition of an AE or SAE and remain responsible for following up on AEs that are serious, considered related to the study device or the study, or that caused the participant to discontinue the study.

6.3.1 Time Period and Frequency for Collecting AE and SAE Information

All AEs and SAEs will be collected from randomization until the end of the study at the timepoints specified in the SoA.

All SAEs will be recorded and reported to the Sponsor or designee within 24 hours, as indicated in

Appendix . The Investigator will submit any updated SAE data to the Sponsor within 24 hours of it being available.

Investigators are not obligated to actively seek AEs or SAEs after the conclusion of study participation. However, if the Investigator learns of any SAE, including a death, at any time after a participant has been discharged from the study, and he/she considers the event to be reasonably related to the study or study participation, the Investigator must promptly notify the Sponsor.

The method of recording, evaluating, and assessing causality of AEs and SAEs and the procedures for completing and transmitting SAE reports are provided in

Appendix .

6.3.2 Method of Detecting AEs and SAEs

Care will be taken not to introduce bias when detecting AEs and/or SAEs. Open-ended and non-leading verbal questioning of the participant is the preferred method to inquire about AE occurrence.

6.3.3 Follow-up of AEs and SAEs

Ongoing AEs and SAEs will be followed until resolution or stability as determined by the Investigator.

6.3.4 Regulatory Reporting Requirements for SAEs

Prompt notification (within 24 hours, see

Appendix) by the Investigator to the Sponsor of an SAE is essential so that legal obligations and ethical responsibilities towards the safety of participants and the safety of a study treatment under clinical investigation are met.

The Sponsor has a legal responsibility to notify both the local regulatory authority and other regulatory agencies about the safety of a study treatment under clinical investigation. The Sponsor will comply with country-specific regulatory requirements relating to safety reporting to the regulatory authority and IRB.

Investigator safety reports must be prepared for suspected unexpected serious adverse reactions (SUSAR) according to local regulatory requirements and Sponsor policy and forwarded to Investigators as necessary.

7 Statistical Considerations

7.1 Sample Size Determination

The present study will be treated as a non-inferiority trial. An expected standard deviation of AHI between CPAP and TPAP of 12 requires 52 total participants to have 80% power using a 1-sided 2.5% significance level, which accounts for a 5% dropout rate.

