2.1 Study Rationale

A device able to provide inspiratory positive airway pressure (PAP) < expiratory PAP, designated TPAP, is being developed by SleepRes for the treatment of obstructive sleep apnea (OSA). In prior studies, the administration of higher inspiratory than expiratory PAP did not substantially increase treatment efficacy or adherence to continuous PAP (CPAP), which remains low. In our recent investigation, we demonstrated that the addition of a resistor to the CPAP circuit to reduce inspiratory PAP increased subjective comfort. The present study, TheraPAP Equivalence, is a Crossover study designed to examine whether TPAP is equivalent to CPAP in the treatment of OSA.

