2.2.3 Biological Rationale

TPAP is an innovative device/algorithm designed to deliver a lower inspiratory than expiratory PAP. The drop in inspiratory pressure can be modulated during the inspiratory phase. Previous research has shown that reducing inspiratory PAP by placing a resistor in the inspiratory line can enhance subjective comfort and decrease leaks when compared to CPAP, despite maintaining a similar residual apnea-hypopnea index (AHI). However, the resistor could only provide a fixed inspiratory PAP reduction based on existing PAP settings. TPAP addresses this limitation by allowing for adjustable drops in inspiratory PAP throughout the inspiration phase, offering a potentially more personalized and adaptive therapeutic approach.

3 Endpoints

	Endpoints
Primary	
 • TPAP vs. CPAP AHI
Secondary	
 • TPAP vs. CPAP NREM and REM AHI⁴ • TPAP vs. CPAP NREM and REM AHI in supine and lateral position⁵ • TPAP vs. CPAP Sleep efficiency, sleep stage distribution, sleep onset latency, arousal index • TPAP vs. CPAP Unintentional mask leaks • Subjective preference of TPAP vs CPAP • Subjective sleep quality
Safety Endpoints⁶	
 • Spontaneous adverse events

4 Study Design

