7.3 Populations for Analyses

For the purposes of analysis, the following analysis sets are defined:

Set	Description
Randomized	All participants who were randomized.
Modified Intent to Treat (mITT) Set	The mITT set comprises all participants who are randomized, undergo at least 1 h in any study arm, and have at least 1 measurement on the primary endpoint. Participants will be analyzed for equivalence.
Safety Set	The Safety Set consists of all participants who are randomized and undergo at least 1 h in any study arm.
Per Protocol (PP) Set	The PP Population consists of all participants without any major protocol violations and have considered to be evaluable for study analysis.

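### The trial is sized for non-inferiority but is to be analysed for equivalence, and no margin, assumed difference or decision rule is given, so 52 participants and 80% power cannot be reproduced

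*Combined protocol and SAP*

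**What the plan says.** All references are to the combined protocol and SAP.

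- **Section 7.1, framework:** "The present study will be treated as a non-inferiority trial".
- **Section 7.1, sizing:** "An expected standard deviation of AHI between CPAP and TPAP of 12 requires 52 total participants to have 80% power". The test is one-sided at 2.5%, and the total allows for 5% of participants dropping out.
- **Section 7.3, mITT row:** "Participants will be analyzed for equivalence". This is the only instruction on how efficacy is to be analysed.
- **Section 2.1:** the study is "designed to examine whether TPAP is equivalent to CPAP in the treatment of OSA". The study name also contains the word equivalence.
- **Section 3, primary endpoint:** "TPAP vs. CPAP AHI", with no effect measure and no threshold.

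Section 7 covers sample size, randomization, analysis sets and interim analyses. It contains no margin, assumed true difference, primary analysis method or criterion for success. None of its text is marked as redacted.

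**The concern.** Non-inferiority has to exclude only that TPAP is worse than CPAP by the margin or more. Equivalence has to exclude a difference of that size in either direction. At the same margin and the same alpha per side, equivalence is therefore the harder claim, and the 80% in Section 7.1 does not carry over to the analysis named in Section 7.3.

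The larger gap is the missing margin. Either conclusion is defined by its margin, and without one the primary hypothesis cannot be tested. The same confidence interval for the AHI difference could be called a success or a failure, depending on which framework and which margin were chosen after the results were known. A reader could not show that the choice had been made in advance, and the power of either test cannot be checked.

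**Working it through.** **Inputs from the documents.** Section 7.1 gives SD 12 events/h, power 80%, one-sided alpha 2.5%, dropout 5% and N = 52. The design is a within-participant crossover (Section 4.1). Evaluable participants: 52 × 0.95 = 49.4, taken as 49.

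**Inputs not in the documents, so assumed below.** The margin M, the true mean difference d (TPAP minus CPAP AHI, positive meaning TPAP is worse), and that 12 is the SD of the within-participant difference.

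**1. Trying to reproduce 52.** For a paired non-inferiority test,

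n = [SD × (z₀.₉₇₅ + z₀.₈₀) / (M − d)]²

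With SD = 12 and 1.960 + 0.842 = 2.802, M − d remains unknown, so n cannot be evaluated. Solving backwards from n = 49:

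M − d = 12 × 2.802 / √49 = 4.80 events/h (normal), or 4.90 with the noncentral t.

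One round value comes close. M = 5 with d = 0 gives 48 evaluable by the t calculation, and 48 / 0.95 = 50.5, so 51 enrolled. The normal formula gives 46 evaluable and 49 enrolled.

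**2. Sensitivity to the margin** (d = 0, SD 12; power with 49 evaluable; non-inferiority by noncentral t, equivalence by two one-sided t-tests):

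| Margin | Non-inferiority power | Equivalence power, 2.5% per side | Equivalence power, 5% per side | Evaluable (enrolled) for 80% non-inferiority power |
|---|---|---|---|---|
| 3 | 40% | 1% | 9% | 128 (135) |
| 4 | 63% | 26% | 49% | 73 (77) |
| 5 | 81.5% | 63% | 78% | 48 (51) |
| 6 | 93% | 86% | 93% | 34 (36) |

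**3. Non-inferiority against equivalence at the implied margin.** For each assumed d, the margin is the one that gives 80% non-inferiority power with 49 evaluable:

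| Assumed d | Implied margin | Equivalence power, 2.5% per side | Equivalence power, 5% per side |
|---|---|---|---|
| −1 | 3.90 | 19% | 39% |
| 0 | 4.90 | 60% | 76% |
| +1 | 5.90 | 78% | 87% |

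The 60% can be checked by hand. At d = 0 the interval misses each limit with probability 20%, and the two misses almost never occur together, so power is about 100% − 20% − 20% = 60%.

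At d = 0 with 49 evaluable, equivalence reaches 80% power only at a margin of about 5.67 (2.5% per side) or 5.09 (5% per side).

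**4. Sensitivity to the assumed difference.** At M = 5, moving d from 0 to +1 raises the enrolment needed for 80% non-inferiority power from 51 to 77. With 49 evaluable, power falls from 81.5% to 63%.

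**5. Sensitivity to the meaning of the SD.** If 12 is the SD within each condition, with correlation ρ between conditions, the SD of the difference is 12 × √(2(1 − ρ)), and the implied margin at d = 0 is 4.90 × √(2(1 − ρ)). For ρ = 0, 0.25, 0.5 and 0.75 this gives 6.93, 6.00, 4.90 and 3.47.

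**The case against.** The strongest reply is that Section 7.1 is the only explicit statement of the statistical framework and that its one-sided 2.5% test matches it. On this reading, equivalence in Section 7.3 is loose wording that echoes the study's name, Section 2.1 is only rationale, and a margin of 5 with zero difference nearly recovers 52. Section 2.2.3 reports a similar residual AHI with an inspiratory resistor, which fits an assumption of zero difference. Blinded scoring (Section 6.1), no interim analysis (Section 7.4) and approval of amendments (Appendix 1, item 8) also limit the room for post hoc choices.

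Part of this stands:

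- The number 52 has not been shown to be wrong.
- The equivalence powers depend on assumptions that the plan does not make. The 19% needs an assumed TPAP advantage of 1 event/h, and at 5% per side with d = +1 equivalence power is above 80%. The zero-difference case is the fairest single illustration.
- In a crossover, the SD of 12 most naturally means the SD of the difference, so that point calls only for clarification.
- A possible post hoc choice is a weakness of the plan and not evidence of intent.

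The main point is untouched. Section 7.3 tells the analyst what to do, and it conflicts with Section 7.1. Correcting that word would still leave no margin. A margin inferred from the sample size carries no clinical justification and binds nobody, and none of the safeguards listed sets one.

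**Conclusion.** The concern holds and must be fixed. The plan names two different objectives and gives no threshold or rule for either, so neither the sample size nor the power can be verified and no non-inferiority or equivalence conclusion follows from the plan as written.

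The size of the effect can only be illustrated. With 49 evaluable, an SD of the difference of 12 and zero true difference, a trial with 80% non-inferiority power (implied margin 4.9) has 60% power for equivalence at 2.5% per side and 76% at 5% per side. Non-inferiority power itself runs from 40% to 93% as the margin goes from 3 to 6. These margins and the zero difference are assumptions, not figures from the documents.

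**What to change.** Make these changes before any AHI data by treatment are examined.

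1. **Use one objective throughout.** To match Section 7.1, replace equivalence with non-inferiority in the mITT row of Section 7.3, and equivalent with non-inferior in Section 2.1.
2. **Complete Section 7.1.** State the margin actually used in the sizing with its clinical justification (not one solved back from 52), the assumed true difference, and that 12 is the SD of the within-participant difference, if that is what it is.
3. **State the rule.** TPAP is non-inferior if the upper limit of the two-sided 95% confidence interval for mean TPAP minus CPAP AHI lies below the margin.
4. **Restate the power where needed.** If equivalence is kept, give the two-sided limits and the alpha per side, and report the power that 52 participants provide. Do the same if the justified margin is smaller than the one used for sizing, which is inferred here to be about 4.9 at zero difference.

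**Cost.** Wording only, if a justified margin supports 52. Otherwise the stated power falls or the sample grows. For example, at zero difference and SD 12, a margin of 4 would need 73 evaluable (77 enrolled) for 80% non-inferiority power. If equivalence is kept, the stated power may be less favourable: at an assumed margin of 5, equivalence at 2.5% per side would need about 63 evaluable (63 / 0.95 = 66.3, so 67 enrolled).
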